6.2 Background

Paediatric audiologists rely on a battery of audiological tests to characterise the degree (mild through to profound) and nature (e.g., sensorineural vs auditory neuropathy) of hearing loss in infants (AAA 2020). Key amongst these tests are the electrophysiological measures, auditory brainstem response (ABR) and auditory steady state response (ASSR), which can be used to estimate hearing acuity at different frequencies of sound and to determine the nature of any hearing loss (Sininger, Hunter et al. 2020). However, audiologists have long recognised the absence of a key element vital for clinical decision making, namely an objective measure of speech discrimination for infants, and support the development of a clinically viable objective measure for inclusion in the existing test battery (JCIH, 2019).

Speech discrimination information is critical to a detailed understanding of hearing dis/abilities. In older children and adults, it is gained through behavioural testing and is a critical element when deciding rehabilitation strategies. For example, the decision to recommend a cochlear implant for an adult is based in great part on their measured ability to understand speech (Leigh, Dettman et al. 2016, van der Straaten, Briaire et al. 2020). Despite decades of research, and two candidate techniques (mismatch response and acoustic change complex, (Wable, van den Abbeele et al. 2000, Uhler, Hunter et al. 2018), there is still no test of speech discrimination that can be used in the infant diagnostic audiology clinic. Consequently, paediatric audiologists are compelled to make recommendations based primarily on hearing acuity (AAA 2013), or to wait until behavioural results become available. The latter option has the obvious disadvantage of delaying effective habilitation by many months and undermines the rationale of early diagnosis through newborn hearing screening (Ching, Dillon et al. 2018).

Our completed research with the NIRx system is summarised in our paper (McKay, Wunderlich et al. 2023)). Essentially, our novel test procedures and analysis algorithms were shown to provide test accuracies as follows:

- Detection of speech sounds at 65 dB SPL: sensitivity 97%, specificity 100%
- Discrimination of “Ba” from “Ga” at 65 dB SPL: sensitivity 78% specificity 100%

The average haemodynamic response waveform shapes generated by the detection and discrimination testing are shown in Fig. 1 and 2, respectively.

[figure not shown]

Figure 1 Average response waveforms in left and right temporal areas (LT, LR) and left and right prefrontal areas (LPF, RPR) in response to detection of “Ba” at 65 dB SPL. The grey shaded region is the duration of the stimulus in the silence baseline.

[figure not shown]

Figure 2 Average waveforms of responses (changes in HbO (solid) and HbR (dotted)) to discrimination of “Ba” from “Tea”, “Bee”, and “Ga”. Grey shaded region is the duration of the novel stimulus in the non-silence baseline.

Given the success of our development of this fNIRS test, we have built a prototype system (EarGenie MVP) that can automatically run the tests and generate results so that clinicians can easily perform the tests. In this clinical trial, we aim to confirm its safety and basic functionality before performing further clinical studies and trials with EarGenie MVP. The Investigator Brochure outlines how EarGenie MVP functions, is designed, and its safety features.

7 RISK/BENEFIT ASSESSMENT

7.1 Known potential risks

- We do not anticipate any adverse events directly related to the protocol procedures. fNIRS measurements have been safely used in research studies in paediatric populations across the world for many years, and in our laboratory for the past five years, without adverse events. It is a safe technology suitable for use in infants. Other test procedures, such as otoscopy and tympanometry or head circumference measurements, are standard clinical procedures which do not cause discomfort and are not expected to cause distress.
- The EarGenie MVP has been designed by a medical device prototyping company to be safe. It has no mains power attached to any part that is in contact with the infant. The montage contains a 3.7V lithium polymer (LiPo) battery (see Investigator’s Brochure for details), which is not in contact with the infant, and can only be recharged using a dedicated charging cradle (i.e., it is impossible to attempt to charge the battery while on the infant’s head). The headgear communicates to the dedicated computer via Bluetooth. Only the headband and montage cover are in contact with the infant. The headband is made from soft medical grade material (see IB) and the optode montage is covered with a thin flexible single-use cover made from TPU (Thermoplastic Polyurethane), a material commonly used in healthcare applications, with no known aggravation effects. To mitigate cross-infection risk, the montage

covers are designed to be single use, and the headband is wipeable with alcohol wipes or similar after each use.

- Our clinical team is led by an expert paediatric audiologist with over 35 years' experience in infant diagnostics; all testers are either qualified audiologists or trained and directly supervised during testing (at elbow) by qualified audiologists.
- The fNIRS test can only be carried out if the infant is either asleep or quietly being entertained. Testing will be discontinued if the baby becomes distressed and cannot be resettled at any time.

Discomfort or skin damage from headgear

We expect that babies will not experience discomfort from wearing the headgear, which holds the optical emitters and detectors and electronics. It is made up of a headband made from a soft material which is easily fitted on the infant's head using low profile velcro hooks that are easy to adjust and undo. The montage containing the optodes is a flexible, moulded assembly which clips into the headband. The only parts of the headgear that contact the baby's scalp are the head band and the flexible montage cover. There are no cables to hinder movement or cause entanglement.

The headgear can be positioned before the baby is settled to sleep or once they are asleep. Our experience, gained by testing over 100 babies with our research device (NIRx NIRScout) and a cap covering the whole head, is that placement causes only minor disturbance, and that the great majority of babies continue to sleep once it is placed. We reasonably expect that babies will experience less disturbance with this more comfortable headgear than from the NIRx research device.

The case report form for each infant will capture any discomfort or observable effects on the baby's skin as this study's primary outcome measures (along with any unexpected adverse events).

Time and travel

We schedule a 2-hour appointment for the test session and recognise that this is a substantial time commitment for a family with a young baby. As experienced audiologists we are sensitive to this and make every effort to schedule appointments that are convenient for the family. Families are reimbursed their travel expenses and provided with free onsite parking.

Sound levels

Our test protocols use soft to comfortably loud level sounds and do not involve high-level sounds, however it is recognised that there is potential for their accidental presentation due to operator or technical error. To avoid this potential risk, all sounds, which are stored digitally as .wav files, are measured using a calibrated sound level meter at the time that the protocol is developed. On the day of testing the pre-test protocol involves both listening to the sounds and measuring them with a sound level meter to ensure that there are no sound artifacts and that presentation levels are correct.

7.2 Known potential benefits

There is no benefit of participation to the normal hearing infants. The benefit of this clinical trial is in the development of a clinical hearing device to improve the management of babies with hearing loss and thereby facilitate their language development.

7.3 Assessment of potential risks and benefits

Overall, the risks of participation are limited, and mainly relate to time and potential discomfort. The benefits of the study, in terms of development of a clinical fNIRS device to inform management of hearing-impaired infants and prevent or reduce language delay, outweighs the possible risks.

8 TRIAL OBJECTIVES AND OUTCOMES

8.1 Objectives

8.1.1 Primary objective

The primary objective of this trial is to establish the safety and comfort of EarGenie MVP.

8.1.2 Secondary objective

The secondary objective of this trial is to obtain preliminary evidence that the test results obtained when using EarGenie MVP to test normally-hearing infants are largely consistent with those obtained by a cohort of 36 normally-hearing infants previously tested in our lab with the NIRx NIRScout continuous wave near infrared spectrometer.

8.2 Outcomes

Table listing objectives and outcomes.

OBJECTIVE	OUTCOME & OUTCOME MEASURE
Primary	
The primary objective of this trial is to establish the safety and comfort of EarGenie MVP.	The intended outcome is that EarGenie MVP is safe and comfortable for use in human infants. The measure is the incidence of any adverse events recorded (safety) and incidence of discomfort. The measures of discomfort will include observations of crying, attempts to remove headgear, verbal indications of distress (in an infant with developed speech), and observations of any marks left by the headgear on the skin, along with the duration (in minutes) of such incidents. The summary report will be presented as incidence of such events along with their duration, and a full description of each incident.
Secondary	
The secondary objective of this trial is to obtain preliminary evidence of device feasibility by showing that the test results obtained when using EarGenie MVP to test normally-hearing infants are largely consistent with those obtained by a cohort of 36 normally-hearing infants previously tested in our lab with the NIRx NIRScout continuous wave near infrared spectrometer.	The secondary outcome is that the test results obtained with EarGenie MVP are largely consistent with the sensitivity and specificity of the test results formerly obtained with our NIRx NIRScout research device in normal-hearing infants, thus confirming the suitability of EarGenie MVP for further clinical studies. The outcome measure is the proportion of babies who show a significant detection and discrimination response and also produce fNIRS average waveforms with shape consistent with those shown in the previous studies. Specifically, we expect that at least 9/10 infants (90%) will show a significant detection response for “Ba” at 65 dB SPL, and that their average waveforms for

OBJECTIVE	OUTCOME & OUTCOME MEASURE
	
this test should consist of a positive HbO peak around 5-8 s latency, or a negative HbO response with latency 12-16 s, or a shape consistent with a combination of these shapes (refer to Figure 1).
 
For the test of discrimination of “Ba” from “Ga”, we expect that at least 7/10 infants (70%) will show a significant discrimination response, and that their average response waveforms should consist of a positive HbO response with latency 6-12 s or a negative HbO response with latency 12-20 s, or a combination of both these shapes (Figure 2).

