2 PROTOCOL SYNOPSIS

Title	EarGenie assessment of a minimum viable product (MVP): a first in human trial of an fNIRS measure of sound detection and speech discrimination in normal hearing infants
Trial Description	This is a first-in-human clinical trial of EarGenie minimum viable product (MVP).
Objectives	
The primary objective of this trial is to establish the safety and comfort of EarGenie MVP.
 
The secondary objective of this trial is to obtain preliminary evidence that the test results obtained when using EarGenie MVP to test normally-hearing infants are largely consistent with those obtained by a cohort of 36 normally-hearing infants previously tested in our lab with the NIRx NIRScout continuous wave near infrared spectrometer.

Outcomes and Outcome Measures	
The primary outcome is that EarGenie MVP is safe and comfortable for use in human infants. The measure is documentation of any adverse events (safety) or discomfort (e.g., crying, not settling to sleep) shown by the baby when wearing the device.
 
The secondary outcome is that the test results obtained with EarGenie MVP are largely consistent with the sensitivity and specificity of the test results formerly obtained with our NIRx NIRScout research device in normal-hearing infants, thus confirming the suitability of EarGenie MVP for further clinical studies. The outcome measure is the proportion of babies who show a significant detection and discrimination response and also produce fNIRS average waveforms with shape consistent with those shown in the previous studies. To be consistent with the NIRx results we would require not more than 1(/10) baby (or 10%) to have an absent detection response at 65 dB SPL and not more than 3 (/10) babies (or 30%) to show an absent discrimination response for “Ba” versus “Ga”.

Trial Population	Ten infants with normal hearing
Description of sites enrolling participants	This trial will be conducted at the Bionics Institute, [name].

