9 TRIAL DESIGN

9.1 Overall design

This is a first-in-human trial of a new medical device prototype (EarGenie MVP). Ten infants with normal hearing will be tested with EarGenie MVP, to confirm the safety and comfort of EarGenie MVP for infants. The results of the fNIRS tests of speech sound detection and discrimination in these infants will be used to confirm the functionality of EarGenie MVP and to obtain preliminary evidence that the test results that it outputs are consistent with the results obtained previously for 36 normal hearing infants (aged 2-20 months) using our research device NIRx. The NIRx device (NIRx NIRScout) a research device with CE marking. Those infants produced fNIRS responses of shapes with predictable characteristics that did not vary with age or between infants. Because of this consistency across age and individuals, we are confident that comparison of the new data with the previous data will enable us to determine preliminary device feasibility.

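### The secondary outcome claims consistency with the NIRx specificity, but nothing in the plan measures false positives; the wording should be limited to response rate and waveform shape.

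*Combined protocol and SAP*

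**What the plan says.** Section 8.2, and the synopsis in the same words, describe the secondary outcome as results that are "largely consistent with the sensitivity and specificity of the test results formerly obtained with our NIRx NIRScout research device". The benchmark is in section 6.2: "sensitivity 97%, specificity 100" per cent for detection at 65 dB SPL, and "sensitivity 78% specificity 100" per cent for Ba versus Ga. That section does not say how the specificity was obtained or on how many tests.

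The measure attached to this outcome is the proportion of infants with a significant detection and discrimination response who "also produce fNIRS average waveforms with shape consistent with those shown in the previous studies". Sections 8.2, 12.3 and 16.3 set the expected counts at 9 or more of 10 for detection and 7 or more of 10 for discrimination, with latency windows for the HbO waveform. The synopsis gives the same limits from the other side: "To be consistent with the NIRx results we would require not more than 1(/10) baby (or 10%) to have an absent detection response", and no more than 3 of 10 without a discrimination response.

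On the population, section 9.1 says "Ten infants with normal hearing will be tested with EarGenie MVP", and section 16.3 expects these infants both to hear and to discriminate the sounds. The secondary objective in section 8.1.2 is looser than the outcome. It asks for results "largely consistent with those obtained by a cohort of 36 normally-hearing infants previously tested in our lab" and does not mention specificity.

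**The concern.** Specificity is the proportion of negative-condition tests that return a negative result. For this device a negative condition is a run with no sound (detection) or no change of sound (discrimination), or an infant who cannot hear or discriminate the stimulus. The protocol describes none of these. The outcome therefore names a property on which the planned analysis produces no data.

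If 9 of 10 and 7 of 10 are reached with fitting waveforms, the outcome as worded would allow a statement of consistency with a specificity of 100%, without one test in which a false positive could have occurred. Sections 8.2 and 21 use the result to support taking the device into further clinical studies, and section 21 says the results will be posted on the registry. For a hearing test, a false positive means reporting that an infant heard or distinguished a sound when that did not happen, so this property should not be implied without data.

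**Working it through.** **1. The plan's own figures.** Section 16.1 gives no sample-size calculation, so there is none to reproduce. Taking the cohort size of 36 as the denominator (an assumption), the NIRx sensitivities fit 35/36 = 97.2% and 28/36 = 77.8%. The 100% specificity cannot be reproduced, because neither the number nor the type of negative tests is given. If it were 36/36, the 95% upper bound on the false-positive rate would be 1 − 0.05^(1/36) = 8.0% one-sided, or 1 − 0.025^(1/36) = 9.7% two-sided.

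**2. Planned tests by correct answer.**

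| Test (section 12.3) | Infants | Correct answer: response | Correct answer: no response |
|---|---|---|---|
| Detection of Ba, 65 dB SPL | 10 | 10 | 0 |
| Ba versus Ga | 10 | 10 | 0 |
| Total | | 20 | 0 |

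Specificity = true negatives / negative-condition tests = 0/0, which is not estimable. Twenty is a maximum, since section 12.5.5 lets an infant complete with partial results; the zero does not depend on it.

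**3. Other possible sources of negative tests.**
- *Extra recording time.* Section 12.3 fills it with further speech at comfortable levels and leaves those responses out of the main outcome analysis.
- *Silent segments.* The caption to the earlier NIRx detection figure in section 6.2 says "The grey shaded region is the duration of the stimulus in the silence baseline", so silent stretches may also exist in the EarGenie recordings. No section plans to analyse them as no-sound tests.
- *Waveform shape.* This is judged only on runs with real sound, so it has no negative-condition denominator.

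**4. Does specificity affect whether the thresholds are met?** Take a device with the NIRx sensitivities. Require each counted infant to have both a significant response and a fitting waveform, and let c be the share of true responses that fit. The documents give no value for c; 100%, 95% and 90% are assumed. The two tests are assumed independent. With X binomial on n = 10:

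P(both met) = P(X ≥ 9 | 0.97c) × P(X ≥ 7 | 0.78c)

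For example, at c = 1, P(X ≥ 9) = 10 × 0.97^9 × 0.03 + 0.97^10 = 0.2281 + 0.7374 = 0.9655.

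| c | Detection, 9 or more of 10 | Discrimination, 7 or more of 10 | Both |
|---|---|---|---|
| 1.00 | p = 0.970: 0.9655 | p = 0.780: 0.8413 | 0.812 |
| 0.95 | p = 0.9215: 0.8176 | p = 0.741: 0.7545 | 0.617 |
| 0.90 | p = 0.873: 0.6312 | p = 0.702: 0.6549 | 0.413 |

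No term contains specificity, so each row is the same whether the device's specificity is 100%, 50% or 0%. This holds the results on real-sound runs fixed. At the extreme, a device that always reports a response (specificity 0%) meets both response counts with probability 1, waveform condition aside. How often an over-calling device would also pass the waveform condition cannot be worked out from the documents.

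**The case against.** The strongest reply is that the disputed phrase only frames the outcome, and the plan then says what it means. The next sentence in section 8.2 defines the measure as responses plus waveform shape, the synopsis defines consistency through limits on absent responses, and sections 12.3 and 16.3 never mention specificity. No threshold or summary uses it, and section 16.1 calls the evidence preliminary. This stands as a reason to rate the point minor. It does not remove the mismatch: the stated outcome still includes a property that its own measure cannot address.

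A second reply is that the waveform condition guards against false positives. It may catch some, but it gives no rate to set beside 100%.

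Third, the cited NIRx paper, the Investigator's Brochure and the stimulus presentation protocol mentioned in section 14.2.6 are not available here, and a no-sound run might be described in one of them. That is fair. What can be said is that this protocol, including its statistical section, specifies no such run and no false-positive analysis.

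Fourth, the probabilities in the second table rest on assumed waveform-fit shares, and their constancy across specificity follows from how they are set up. Also fair: they illustrate the point, and the argument rests on the count of zero.

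Finally, the word could be kept by adding a no-sound or no-change run, or a prespecified analysis of silent segments. That is a legitimate alternative, weighed under the fix.

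**Conclusion.** The concern holds and is minor. The secondary outcome claims consistency with a specificity of 100%, while 0 of at most 20 planned main results come from a condition in which no response is correct. The data can speak to response rate and waveform shape; on specificity they leave the whole range from 0% to 100% open. This conclusion needs only the population, the two main tests and the analysis as described, plus the plan's own expectation that every infant hears and discriminates the sounds. The illustrative probabilities of 0.81, 0.62 and 0.41 rest further on the assumed fit shares, per-infant scoring of waveforms and independence of the two tests. The primary safety outcome, the sample size and the thresholds are unaffected.

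**What to change.** In the synopsis and in section 8.2, delete the words *and specificity*, so that the comparison is with the NIRx sensitivity only, alongside the waveform-shape condition already in the outcome measure. Add one sentence in both places: *False-positive responses (specificity) are not evaluated in this trial.* The outcome then no longer claims a property that the objective in section 8.1.2 does not mention.

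The cost is a wording change in two places and a narrower claim. Procedures, infants, data, thresholds and analysis stay as they are. If the change is treated as an amendment, section 17.2 requires HREC approval before it is implemented.

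If the sponsor prefers to keep specificity, a negative-condition test and a false-positive count must be prespecified. That adds an analysis and, if new runs are needed, a procedure, and it would give little precision. With one such run per infant (assumed) and no false positives in 10, the 95% upper bound on the false-positive rate would be 1 − 0.05^(1/10) = 25.9% one-sided, or 1 − 0.025^(1/10) = 30.8% two-sided. The wording change suits the existing design better.

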9 TRIAL DESIGN

9.1 Overall design

This is a first-in-human trial of a new medical device prototype (EarGenie MVP). Ten infants with normal hearing will be tested with EarGenie MVP, to confirm the safety and comfort of EarGenie MVP for infants. The results of the fNIRS tests of speech sound detection and discrimination in these infants will be used to confirm the functionality of EarGenie MVP and to obtain preliminary evidence that the test results that it outputs are consistent with the results obtained previously for 36 normal hearing infants (aged 2-20 months) using our research device NIRx. The NIRx device (NIRx NIRScout) a research device with CE marking. Those infants produced fNIRS responses of shapes with predictable characteristics that did not vary with age or between infants. Because of this consistency across age and individuals, we are confident that comparison of the new data with the previous data will enable us to determine preliminary device feasibility.

